4.2.10.8 Laboratory evaluation

Laboratory evaluations are described in section 3.3.5.2. Baseline and post-baseline definitions are detailed in section 3.1.2. All tables and listings for laboratory data will be based on the as-treated population and presented for each treatment group in IDMC reports and at final analysis.

Laboratory test results for haematology, coagulation and clinical chemistry quantitative parameters will be summarized, with their units of measure, with n, mean, SD, median, minimum, and maximum at each visit and for change from baseline.

Shifts from baseline to maximum and minimum value during the on-treatment phase will be presented for haematology and clinical chemistry parameters.

All individual laboratory data for haematology, coagulation and clinical chemistry will be also presented in a listing in that order.

In addition to the tables above, as described in the study protocol, also the following will be presented:

- Plots for the maximum on-treatment ALT/maximum on-treatment AST by maximum total bilirubin, expressed as multiples of ULN for assessing Hy's law criteria,
- List of key subject information for subjects with potential Hy's law combined ALT or AST, and bilirubin, and
- Proportion of subjects with elevated liver test based on measured laboratory values

In the 3 tables and figures listed above all measurements including unscheduled visits will be taken into account.

Elevated liver tests are defined as elevations from baseline up to the end of the study as follows:

ALT elevations

- ALT > 3xUpper Limit of Normal (ULN)
- ALT > 5xULN
- ALT > 10xULN
- ALT > 20xULN

AST elevations

- AST > 3xULN
- AST > 5xULN
- AST > 10xULN
- AST > 20xULN

AST or ALT elevations

- ALT or AST > 3xULN
- ALT or AST > 5xULN
- ALT or AST > 10xULN
- ALT or AST > 20xULN

Total bilirubin (BILI) elevations

- BILI > 1.5xULN
- BILI > 2xULN

(ALT or AST elevations) and BILI elevation

- (ALT > 3xULN or AST > 3xULN) and (BILI > 1.5xULN within 14 days on or after ALT or AST elevation)
- (ALT > 3xULN or AST > 3xULN) and (BILI > 2xULN within 14 days on or after ALT or AST elevation)
- (ALT > 3xULN or AST > 3xULN) and ((BILI > 2xULN and no initial ALP \geq 2xULN) within 14 days on or after AST or ALT elevation)

ALP elevations

- ALP > 1.5xULN
- ALP > 3xULN

Occurrences of AST or ALT $\geq 3 \times$ ULN together with total bilirubin $\geq 2 \times$ ULN are reported as SAE (Potential Hy's law) as described in the study protocol.

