Procedure	Visit:	3	4	5	6	7	8	9	10	11	12	Notes	Details in CSP section or appendix
	Day (± 7): ^a	1	10 ^a	29	57	85	113	141	169	197	225		
Physical examination		X										Abbreviated; includes weight	Section 8.2.1
Vital signs		X	X	X	X	X	X	X	X	X	X	When vital signs and blood draws are scheduled for the same nominal time, blood draws should occur last. The timing of vital signs should allow the blood draw (eg, PK blood sample) to occur at the assigned nominal time.	Section 8.2.2
ECG		X	X	X	X		X		X			The timing of ECGs should allow the blood draw (eg, PK blood sample) to occur at the assigned nominal time. ECGs can occur at any time relative to dosing and will be interpreted locally.	Section 8.2.3

Table 4 Schedule of Activities: Intervention Period

Procedure	Visit:	3	4	5	6	7	8	9	10	11	12	Notes	Details in CSP section or appendix
	Day (± 7): ^a	1	10 ^a	29	57	85	113	141	169	197	225		
Collect blood for:													
Clinical safety (hematology and clinical chemistry)		X	X	X	X		X		X			Must be collected before dosing study intervention.	Section 8.2.4
PK		X	X	X	X		X		X			Must be collected before dosing study intervention.	Section 8.5.1
CCI		X	X	X	X		X		X			Must be collected before dosing study intervention.	Section 8.6.1
CCI NT-proBNP		X					X						Section 8.6.1
Circulating biomarkers of inflammation and CV disease		X					X						Section 8.6.1
Genomics Initiative		X										
 Optional; collect sample if participant signed informed consent Samples will be collected before dosing, and stored. If for any reason the sample is not drawn at Visit 3, it may be 	Section 8.7

Table 4 Schedule of Activities: Intervention Period

Procedure	Visit:	3	4	5	6	7	8	9	10	11	12	Notes	Details in CSP section or appendix
	Day (± 7): ^a	1	10 ^a	29	57	85	113	141	169	197	225		
												taken at any visit until the last study visit	
Samples for diagnostic assay development	X						X					Must be collected before study intervention. Samples will be collected and stored.	Section 8.6.1
Immunogenicity	X		X	X		X		X				On dosing visits, must be collected before dosing study intervention.	Section 8.5.2
Collect urine for:													
Future use (optional)	X											Sample will be collected and stored	Section 8.6.2
Randomization	X											To be randomized, baseline CTA must be interpretable.	Section 6.3.1
Study intervention administration	X		X	X	X	X	X	X	X	X	X	Dosing will occur after blood and optional urine samples have been collected	Sections 6.2.3 and 6.2.4

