Table 4 Schedule of Activities: Intervention Period

Procedure	Visit:	3	4	5	6	7	8	9	10	11	12	Notes	Details in CSP section or appendix
	Day (± 7): ^a	1	10 ^a	29	57	85	113	141	169	197	225		
Observational period		X		X								Participant must be in clinic for 2 hours after dosing.	Section 8.2.5.2
Assessment of AEs/SAEs		X	X	X	X	X	X	X	X	X	X		Section 8.3
Concomitant medications		X	X	X	X	X	X	X	X	X	X		Section 6.5
Assess for injection site reactions		X		X	X	X	X	X	X	X	X		Section 8.2.5.3

^a The visit window is ± 7 days for dosing visits and ± 3 days for non-dosing visits (ie, Day 10 [Visit 4]). If a participant is dosed outside of the visit window, he or she should return to the initial planned schedule for subsequent visits.

AE, adverse event; CSP, Clinical Study Protocol; CV, cardiovascular; ECG, electrocardiogram; HIV, human immunodeficiency virus; CCI [REDACTED]

NT-proBNP, N-terminal prohormone brain natriuretic peptide; PK, pharmacokinetic(s); SAE serious adverse event; CCI [REDACTED]

Table 5 Schedule of Activities: Follow-up Period

Procedure	Visit:	13	14	Notes	Details in CSP section or appendix
	Day:	253 (- 4 to + 11 days)	325 (± 7 days)		
End of study visit			X		Section 4.3
Full physical examination			X		Section 8.2.1
Weight			X		Section 8.2.1
Vital signs		X	X	Whenever vital signs and blood draws are scheduled for the same nominal time, the blood draws should occur last.	Section 8.2.2

Table 5 Schedule of Activities: Follow-up Period

Procedure	Visit:	13	14	Notes	Details in CSP section or appendix
	Day:	253 (- 4 to + 11 days)	325 (± 7 days)		
ECGs		X	X		Section 8.2.3
Assessment of AEs/SAEs		X	X		Section 8.3
Concomitant medications		X	X		Section 6.5
Collect blood for:					
Clinical safety (clinical chemistry and hematology)		X	X		Section 8.2.4
PK		X	X		Section 8.5.1
CCI		X	X	Sample collected on Day 325 will be stored.	Section 8.6.1
CCI NT-proBNP		X			Section 8.6.1
Circulating biomarkers of inflammation CV disease		X			Section 8.6.1
Immunogenicity		X	X		Section 8.5.2
Creatinine for calculating eGFR		X		should occur within 30 days before the CTA; either local laboratory or point of care testing can be used.	Section 8.2.4
Collect urine for:					
Future use (optional)		X		Sample will be collected and stored.	Section 8.6.2
Echocardiogram		X			Section 8.1.1 and 8.1.2 (including instructions for repeating uninterpretable

Table 5 Schedule of Activities: Follow-up Period

Procedure	Visit:	13	14	Notes	Details in CSP section or appendix

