Appendix E Actions Required in Cases of Increases in Liver Biochemistry and Evaluation of Hy's Law

E 1 Introduction

This appendix describes the process to be followed in order to identify and appropriately report Potential Hy's Law cases and Hy's Law cases. It is not intended to be a comprehensive guide to the management of elevated liver biochemistries.

Specific guidance on managing liver abnormalities can be found in Section [8.3.6](#).

During the study the investigator will remain vigilant for increases in liver biochemistry. The investigator is responsible for determining whether a participant meets potential Potential Hy's Law criteria at any point during the study.

All sources of laboratory data are appropriate for the determination of Potential Hy's Law and Hy's Law events; this includes samples taken at scheduled study visits and other visits including central and all local laboratory evaluations even if collected outside of the study visits; for example, Potential Hy's Law criteria could be met by an elevated ALT from a central laboratory **and/or** elevated TBL from a local laboratory.

The investigator will also review AE data (for example, for AEs that may indicate elevations in liver biochemistry) for possible Potential Hy's Law events.

The investigator participates, together with the sponsor's clinical project representatives, in review and assessment of cases meeting Potential Hy's Law criteria to agree whether Hy's Law criteria are met. HL criteria are met if there is no alternative explanation for the elevations in liver biochemistry other than DILI caused by the investigational product.

The investigator is responsible for recording data pertaining to Potential Hy's Law/Hy's Law cases and for reporting SAEs and AEs according to the outcome of the review and assessment in line with standard safety reporting processes.

E 2 Definitions

Potential Hy's Law

AST or ALT $\geq 3x$ ULN **together with** TBL $\geq 2x$ ULN at any point during the study following the start of study medication irrespective of an increase in ALP.

Hy's Law

AST or ALT $\geq 3x$ ULN **together with** TBL $\geq 2x$ ULN, where no other reason, other than the investigational product, can be found to explain the combination of increases, eg, elevated ALP indicating cholestasis, viral hepatitis, another drug.

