For Potential Hy's Law and Hy's Law, the elevation in transaminases must precede or be coincident with (ie, on the same day) the elevation in TBL, but there is no specified timeframe within which the elevations in transaminases and TBL must occur.

E 3 Identification of Potential Hy's Law Cases

In order to identify cases of Potential Hy's Law, it is important to perform a comprehensive review of laboratory data for any participant who meets any of the following identification criteria in isolation or in combination:

- ALT \geq 3x ULN
- AST \geq 3x ULN
- TBL \geq 2x ULN

Central Laboratories Being Used:

When a participant meets any of the Potential Hy's Law identification criteria, in isolation or in combination, the central laboratory will immediately send an alert to the investigator (also sent to the sponsor's representative).

The investigator will also remain vigilant for any local laboratory reports where the Potential Hy's Law identification criteria are met; where this is the case, the investigator will:

- Notify the sponsor's representative.
- Request a repeat of the test (new blood draw) by the central laboratory without delay.
- Complete the appropriate unscheduled laboratory eCRF module(s) with the original local laboratory test result.

When the identification criteria are met from central or local laboratory results, the investigator will without delay:

- Determine whether the participant meets Potential Hy's Law criteria (refer to Appendix [E 2](#) for definition) by reviewing laboratory reports from all previous visits (including both central and local laboratory results).

Local Laboratories Being Used:

The investigator will without delay review each new laboratory report and if the identification criteria are met will:

- Notify the sponsor's representative.
- Determine whether the participant meets Potential Hy's Law criteria (refer to Appendix [E 2](#) for definition) by reviewing laboratory reports from all previous visits.
- Promptly enter the laboratory data into the laboratory eCRF.

E 4 Follow-up

E 4.1 Potential Hy's Law Criteria Not Met

If the participant does not meet Potential Hy's Law criteria the investigator will:

- Inform the sponsor's representative that the participant has not met Potential Hy's Law criteria.
- Perform follow-up on subsequent laboratory results according to the guidance provided in the CSP.

E 4.2 Potential Hy's Law Criteria Met

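### The SAP's combined liver-elevation rows require bilirubin within 14 days and strict inequalities, so the table can undercount Potential Hy's Law as the protocol defines it

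*SAP*

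**What the plan says.** Protocol Appendix E 2 defines Potential Hy's Law as AST or ALT at or above 3x ULN together with total bilirubin at or above 2x ULN, "at any point during the study following the start of study medication irrespective of an increase in ALP". The transaminase rise must come first or fall on the same day, but "there is no specified timeframe within which the elevations in transaminases and TBL must occur".

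SAP section 4.2.10.8 presents its liver outputs as following the protocol. Its elevated-liver-test table has three rows combining transaminases with bilirubin:

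- ALT or AST above 3x ULN with bilirubin above 1.5x ULN;
- the 2x version: "ALT > 3xULN or AST > 3xULN) and (BILI > 2xULN within 14 days on or after ALT or AST elevation";
- the 2x version further limited to participants without an initial ALP of 2x ULN or more.

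All three use strict inequalities and the 14-day limit. The same section closes by restating the protocol thresholds with no window and noting that such occurrences "are reported as SAE (Potential Hy's law) as described in the study protocol". SAP section 6, which lists changes from the protocol, does not mention the narrower rule.

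**The concern.** The protocol's definition can be met across visits: Appendix E 3 has the investigator review laboratory reports from all previous visits to decide whether the criteria are met. The SAP's rows only link results up to 14 days apart, and the scheduled samples are mostly much further apart than that. A participant can therefore meet the protocol definition, be reported as a Potential Hy's Law SAE, and appear in no combined row of the table.

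The table goes to the IDMC by treatment group and holds the only planned combined proportions taken directly from measured laboratory values. When the expected count is near 0 or 1, a zero there beside a reported case is a confusing way to show a rare safety signal.

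**Working it through.** **Inputs.** Protocol section 1.3, Table 4, row "Clinical safety (hematology and clinical chemistry", gives Days 1, 10, 29, 57, 113 and 169. Table 5, row "Clinical safety (clinical chemistry and hematology", adds Days 253 and 325. The Table 4 samples carry the note "Must be collected before dosing study intervention", so Day 1 is baseline and lies outside a definition that starts after first dose. For the intervention period, "The visit window is ± 7 days for dosing visits and ± 3 days for non-dosing visits"; Day 10 is the non-dosing visit. Day 253 has a window of -4 to +11 days and Day 325 of ±7 days.

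**Gaps between consecutive post-dose samples.** Nominal gap = later day - earlier day. Shortest in-window gap = earliest allowed later visit - latest allowed earlier visit.

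| Interval | Nominal gap (days) | Shortest in-window gap (days) |
|---|---|---|
| Day 10 to 29 | 19 | 22 - 13 = 9 |
| Day 29 to 57 | 28 | 50 - 36 = 14 |
| Day 57 to 113 | 56 | 106 - 64 = 42 |
| Day 113 to 169 | 56 | 162 - 120 = 42 |
| Day 169 to 253 | 84 | 249 - 176 = 73 |
| Day 253 to 325 | 72 | 318 - 264 = 54 |

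At nominal timing, 0 of 6 gaps are within 14 days. Within windows, only the first two can be. From Day 57 onward, two different scheduled visits can never satisfy the 14-day rule.

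**Visit pairs.** Seven post-dose samples give 7 x 8 / 2 = 28 ordered pairs (transaminase visit on or before bilirubin visit): 7 same-visit and 21 cross-visit. Appendix E 2 admits all 28. At nominal timing the SAP rule admits only the 7 same-visit pairs. Visit windows can add at most two (Day 10 with 29, Day 29 with 57), leaving 21 - 2 = 19 that in-window scheduled samples cannot satisfy. This counts timing combinations; it is not a probability of missing a case.

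**Which participants are affected.** The rule refers to an ALT or AST elevation and does not say the first one. ALT, AST and bilirubin are in the same chemistry panel (Protocol Table 10).

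- ALT above 3x ULN at Day 113 and still above 3x at Day 169, when bilirubin is above 2x: counted, on the Day 169 sample.
- ALT above 3x ULN at Day 113, ALT and AST both at or below 3x at Day 169, when bilirubin is above 2x: meets Appendix E 2, but is in no combined row on scheduled data because the gap is 56 days.
- ALT or AST peaking at exactly 3x ULN: meets Appendix E 2 with a qualifying bilirubin, but is in no combined row. Bilirubin at exactly 2x ULN: not in either 2x row, though it can enter the 1.5x row.

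**Unscheduled samples.** The SAP includes them in these outputs, so a sample inside 14 days can rescue a case. Appendix E 3 asks for a repeat draw when a local result meets an identification criterion. For a central result it specifies an alert and a review of earlier reports. Rescue is possible but not assured.

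**Participants treated before Amendment 2.** The amendment table shows chemistry was also drawn on Days 85, 141, 197 and 225. Assuming Day 169 was drawn as well, nominal gaps from Day 29 to Day 253 were 28 days, still above 14. The documents do not say whether chemistry was drawn at the removed Day 122 visit.

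**The case against.** The strongest reply is that the table is headed as elevated liver tests from measured values and does not claim to count Potential Hy's Law. Appendix E is a process for identifying and reporting cases, and Protocol section 9.4.3 promises only descriptive laboratory summaries. A time-linked category is a legitimate description, and a rule without a window can join unrelated elevations. That stands as a reason to keep the 14-day rows. It does not explain why the protocol's own definition has no row in a section presented as following the protocol.

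A reader might also infer more than the documents support:

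- *That every case spread over two scheduled visits is lost.* It is not: a persistent transaminase elevation qualifies on the later sample, and unscheduled or early-window visits can fall within 14 days.
- *That these are the only between-group figures for the combined signal.* SAE counts and percentages are tabulated by treatment group and preferred term in the IDMC reports. The Potential Hy's Law listing has no stated window. The plot of maximum transaminase against maximum bilirubin ignores order, so it would show a split-visit on-treatment case. The narrower statement holds: these are the only combined proportions derived from laboratory values.
- *That the table always falls below the SAE count.* The 1.5x row can exceed it. Appendix E 5 also lets an SAE's term, causality and seriousness be reassessed once an alternative explanation is agreed, which can lower the SAE count. The two need not agree even with an added row.

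The other outputs do not fully substitute. The listing gives no proportion and no derivation rule. The plot limits transaminases to the on-treatment phase, which ends 28 days after the last dose, so Day 325 is outside it for a participant dosed through Day 225.

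**Conclusion.** The point holds as a possible undercount. The SAP's combined rows are narrower than Appendix E 2 in time and in strictness at the thresholds, with ALP a further restriction in one row; this is not declared as a change. The cases at risk are those in which both transaminases have fallen to 3x ULN or below before bilirubin rises at a later visit with no bridging sample, and those with values exactly at a threshold. The number is expected to be small and the documents give no rate from which to estimate it, but one case matters when the count is 0 or 1. Individual cases should still reach the IDMC by other routes, so this is a cheap improvement to consistency, not a failure of safety reporting. The conclusion assumes the Amendment 2 schedule, visits kept within their windows, and the rule applied to any transaminase elevation. If programmed from the first elevation only, the undercount would be larger.

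**What to change.** Add one row to the elevated-liver-test table in SAP section 4.2.10.8 that reproduces Appendix E 2: ALT or AST at least 3x ULN and total bilirubin at least 2x ULN on the same or any later day, after first dose and up to end of study, irrespective of ALP, with unscheduled samples included. State that the key-subject listing uses the same definition. Keep the three 14-day rows as supplementary.

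The cost is one table row and one sentence, from data already collected. The downside is that the new row may include elevations unrelated in time; the 14-day rows beside it and the listing will show which these are.

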4.2.10.8.1 Handling of results below or above Limit of Quantification (LOQ)

Values lower (or upper) the limit of quantification (LLOQ or ULOQ) will be imputed for summary tables. Original values will be reported in the listings. Imputation will be based on the significant digits reported. The following approach will be taken, with x, y and z representing integers ≥ 1 .

- If the original result is $>x$ or $\geq x$ then the result will be imputed by $x+1$
- If the original result is $>x.y$ or $\geq x.y$ then the result will be imputed by $x.y+0.1$
- If the original result is $>x.yz$ or $\geq x.yz$ then the result will be imputed by $x.yz+0.01$
- Etc

- If the original results is $<x$ or $\leq x$ then the result will be imputed by $x-1$
- If the original results is $<x.y$ or $\leq x.y$ then the result will be imputed by $x.y-0.1$
- If the original results is $<x.yz$ or $\leq x.yz$ then the result will be imputed by $x.yz-0.01$
- Etc

4.2.10.9 Vital signs

Vital signs are described in section 3.3.5.3. Baseline and post-baseline definitions are detailed in section 3.1.2. Vital signs (systolic blood pressure, diastolic blood pressure and heart rate) tables and listings will be based on the as-treated population and presented for each treatment group at final analysis.

Vital signs will be summarized descriptively as continuous variables at each visit and for change from baseline at each post-baseline visit.

All vital signs data will be listed. The listing will include reference ranges and classification of vital signs as normal, low and high.

4.2.10.10 ECG

ECG parameters are described in section 3.3.5.4. Baseline and post-baseline definitions are detailed in section 3.1.2. ECG listing will be based on the as-treated population and presented for each treatment group at final analysis.

Overall evaluation will be listed for subjects with clinically significant abnormalities.

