2.3 Benefit/Risk Assessment

2.3.1 Risk Assessment

Table 6 Risk Assessment

Potential Risk of Clinical Significance	Summary of Data and/or Rationale for Risk	Mitigation Strategy
Study intervention		
Bleeding	
• CCI [REDACTED]• Activated platelets express CCI [REDACTED] and the IgG Fc receptor Fc_YRIIa. There is a hypothetical risk that crosslinking of platelets via Fc receptors could trigger platelet destruction leading to thrombocytopenia (Arman and Krauel 2015), which is a risk factor for bleeding.• There have been no indications of abnormal bleeding in monkeys during toxicity studies with MEDI6570. CCI [REDACTED]	
• Exclusion of participants with a history or presence of known bleeding disorder, active bleeding, or high risk of bleeding, need for chronic anticoagulant therapy or platelet count < 100000 platelets/μL. (Arman and Krauel 2015). Please refer to exclusion criteria (Section 5.2).• Standard hematological safety monitoring, including platelet count (Section 8.2.4), and monitoring participants for bleeding events (Section 8.2.5.1)• Encourage the use of PPIs if the concomitant use of NSAID therapy is required.• All bleeding events will be reported as AEs and characterized further.

Table 6 Risk Assessment

Potential Risk of Clinical Significance	Summary of Data and/or Rationale for Risk	Mitigation Strategy
Hypersensitivity reactions including anaphylactic reactions and immune complex disease	
 Pharmacological administration of any peptide or protein may lead to hypersensitivity reactions including anaphylactic reactions, and of most concern clinically, immune complex disease. CCl [REDACTED] 	
 Exclusion of participants with a known history of hypersensitivity reactions to other biologics, to human IgG preparations, or to any component of MEDI6570 (Section 5.2). Participants will be monitored closely during and after administration of study intervention for hypersensitivity reactions, including monitoring for signs and symptoms of immune complex disease. Severe hypersensitivity reactions should be managed according to standard clinical practice, and medical equipment and staff trained to treat acute anaphylactic reactions must be available at all sites (Section 8.2.5.2). If a hypersensitivity reaction occurs, dosing of the participant will be stopped (Section 7.1).

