3 OBJECTIVES AND ENDPOINTS

In participants with a prior MI, persistent inflammation and elevated NT-proBNP, the following endpoints in [Table 7](#) will be evaluated in order to meet the objectives of the study.

Table 7 Objectives and Endpoints

Objectives	Endpoints
Primary	
To evaluate the effect of MEDI6570 on non-calcified coronary atherosclerotic plaques compared with placebo	Change from baseline to Day 253 in non-calcified plaque volume in the most diseased coronary segment (NCPV _{MD}), as measured by CTA imaging
Secondary	
To evaluate the effect of MEDI6570 on a surrogate biomarker of HF compared with placebo	Relative change from baseline to Day 253 in NT-proBNP.
To evaluate the effect of MEDI6570 on left ventricular systolic function compared with placebo	Change from baseline to Day 253 in: 
 • LVEF • GLS as measured by echocardiography
To evaluate the effect of MEDI6570 on left ventricular systolic function among participants with reduced ejection fraction (defined as < 50%) compared with placebo	Change from baseline to Day 253 in: 
 • LVEF • GLS as measured by echocardiography
To evaluate the effect of MEDI6570 on other measures of non-calcified coronary atherosclerotic plaque compared with placebo	Change from baseline to Day 253 in: 
 • Global non-calcified plaque volume • Low attenuation plaque volume as measured by CTA imaging
To evaluate the immunogenicity of MEDI6570	
 • ADA incidence • Titer as measured in serum during the intervention and follow-up periods
To evaluate the PK of MEDI6570	MEDI6570 concentrations as measured in serum during the intervention and follow-up periods
Safety	
To assess the safety and tolerability of MEDI6570 compared with placebo	During the intervention and follow-up periods: 
 • AEs • Clinically important changes in: 
 Vital signs ECGs Safety laboratory assessments

Table 7 Objectives and Endpoints

Objectives	Endpoints
Exploratory	
CCI	
CCI	

The Day 253 endpoint includes the visit window around Visit 13 of - 4 to + 11 days.

ADA, anti-drug antibody(ies); AE, adverse event; CTA, computed tomography angiography; CV, cardiovascular; ECG, electrocardiogram; CCI [REDACTED]

; GLS, global longitudinal strain; HF, heart failure; CCI [REDACTED]

MI, myocardial

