3.3 Efficacy and safety variables

The primary objective of the study is the evaluation of the effect of MEDI6570 on non-calcified plaque volume in the most diseased coronary segment (NCPV_{MD}) compared with placebo. The effect will be evaluated by using as primary endpoint the change from baseline to Day 253 in NCPV_{MD}, as measured by CTA imaging.

Secondary and Exploratory efficacy endpoints are described in sections [3.3.2](#) and [0](#).

Additional secondary objectives are the evaluation of pharmacokinetics (PK) and immunogenicity of MEDI6570. Furthermore, the safety of MEDI6570 compared with placebo will be explored in terms of adverse events (AE) including serious adverse events (SAEs), laboratory evaluations, vital signs, and Electrocardiogram (ECG) analyses.

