3.3.5.4 ECG

Overall ECG evaluation (normal, abnormal) is collected. If abnormal, also reason and clinically significance is collected.

ECG evaluations are assigned as per timepoint related to analysis visits (Table 3).

ECG last observation on treatment is defined as last available value among those in the on-treatment analysis phase.

The analysis will be based on as-treated population.

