4.2.10.7 Adverse events

After having assigned the AEs to the corresponding analysis phase as described in section [3.3.5.1](#), the AEs will be summarized for each treatment group and overall (total will not include placebo subjects). The AEs tables will be based on the as-treated population except the AE by ADA tables which will be based on the Immunogenicity population. Summary tables will include AEs in the on-treatment phase and AEs in the follow-up phase.

Summary tables are listed below.

An overview table containing:

- Number and percentage of subjects with any AEs
- Number and percentage of subjects with any AEs with outcome of death
- Number and percentage of subjects with any SAE (including events with outcome = death)
- Number and percentage of subjects with any AEs leading to discontinuation of treatment
- Number and percentage of subjects with any AEs leading to withdrawal from study

Subjects with multiple events in the same category are counted only once in that category.
Subjects with events in more than 1 category are counted once in each of those categories.

An overview table containing:

- Any AE
- Any AEs with outcome of death
- Any SAE (including events with outcome of death)
- Any AE leading to discontinuation of treatment
- Any AE leading to withdrawal from study

Multiple events in the same category are counted multiple times in that category. Multiple events belonging to more than 1 category are counted multiple times in each of those categories.

The following summary tables will be presented by SOC and PT:

- The number and percentage of subjects with any AEs
- The number of AEs
- The number and percentage of subjects with AEs with outcome of death
- The number of SAEs
- The number and percentage of subjects with SAEs
- The number and percentage of subjects with SAEs, assessed by investigator as possibly related to investigational product
- The number and percentage of subjects with AEs leading to discontinuation
- The number and percentage of subjects with any bleedings (all events from bleeding event form or from adverse event form with SMQ= “Haemorrhages narrow”)
- The number and percentage of subjects with any injection site reactions (all events from ISR form or from adverse event form with HLT= “Injection site reactions”)
- Overall summary of number and percentage of subjects with any AEs by ADA (anti-drug antibody category)
- The number and percentage of subjects by ADA (anti-drug antibody category)

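### The SAP's ECG section plans only a listing, with no by-arm comparison with placebo, and hypersensitivity, a named risk, has no pre-specified grouped adverse event table

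*SAP*

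**What the plan says.** **Objective.** Protocol section 3, Table 7, states the safety objective as "To assess the safety and tolerability of MEDI6570 compared with placebo" and names ECGs among the measures in which clinically important changes are an endpoint. SAP 3.3 repeats the comparative aim: "the safety of MEDI6570 compared with placebo will be explored in terms of adverse events (AE) including serious adverse events (SAEs", and the sentence goes on to name laboratory evaluations, vital signs and ECG analyses.

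**ECG.** SAP 3.3.5.4 collects an overall evaluation (normal or abnormal) and, where abnormal, the reason and clinical significance. It then derives a further variable: "ECG last observation on treatment is defined as last available value among those in the on-treatment analysis phase". SAP 4.2.10.10 plans the output: "ECG listing will be based on the as-treated population and presented for each treatment group at final analysis", and "Overall evaluation will be listed for subjects with clinically significant abnormalities". No other ECG output is named there.

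**Hypersensitivity.** Protocol 2.3.1, Table 6, says that giving any peptide or protein "may lead to hypersensitivity reactions including anaphylactic reactions, and of most concern clinically, immune complex disease". SAP 4.2.10.7 has a by-arm table for bleeding, built from the bleeding form or a MedDRA SMQ. It has another for injection site reactions, built from a dedicated form or a MedDRA HLT ("The number and percentage of subjects with any injection site reactions"). It has no such entry for hypersensitivity.

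**The concern.** A listing restricted to clinically significant cases has no count of subjects with an ECG, no percentage, and no record of who was already abnormal at baseline. If the ECG section is followed as written, the study report will contain no planned ECG comparison with placebo, although both documents say there will be one. ECGs are recorded at nine time points per participant under Amendment 2, so the data exist.

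For hypersensitivity the issue is sensitivity and pre-specification. One reaction type can be coded to several preferred terms. Without an agreed grouping, a modest excess may be spread over rows that each hold only a few subjects, and a grouping chosen after unblinding is open to challenge.

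**Working it through.** The plan states no power or precision figure for safety, so there is none to reproduce. The ECG part is a comparison of texts; the hypersensitivity part is an illustration.

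**1. ECG: planned outputs side by side**

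| Safety measure | By-arm summary | Baseline shift | Section |
|---|---|---|---|
| Laboratory | yes, by visit | yes, haematology and chemistry | SAP 4.2.10.8 |
| Vital signs | yes, by visit | change from baseline | SAP 4.2.10.9 |
| ECG | none named | none named | SAP 4.2.10.10 |

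- ECG time points: screening (1), Visits 3, 4, 5, 6, 8 and 10 (6), and Visits 13 and 14 (2). 1 + 6 + 2 = 9 (Protocol Tables 3 to 5).
- The last on-treatment ECG of SAP 3.3.5.4 feeds no output in 4.2.10.10.
- SAP 4.1 sets general rules: safety endpoints summarised by treatment group and visit, and shift tables for categorical variables. Both are conditional on being appropriate. The specific ECG section names only a listing, and the SAP does not say which text governs.

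**2. Hypersensitivity: what a grouped row adds**

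Inputs:
- 123 per arm: planned randomised number for each continuing dose group and for pooled placebo (Protocol 1.1 and 4.1). The as-treated number is not stated.
- One-sided 0.05 (SAP 4.1), used here only as a yardstick.
- Assumed, not in the documents: subjects with any event, 8% active v 2% placebo; events split evenly over k preferred terms, one term per subject.

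Expected subjects, grouped: 123 × 0.08 = 9.84 active and 123 × 0.02 = 2.46 placebo. With k terms, each row expects 9.84/k and 2.46/k.

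Power is the sum, over all pairs (x, y) whose one-sided Fisher p is at most 0.05, of Bin(x; 123, 0.08/k) × Bin(y; 123, 0.02/k).

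| Rows | Expected per row, active v placebo | Power per row |
|---|---|---|
| 1 (grouped) | 9.84 v 2.46 | 0.60 |
| 2 terms | 4.92 v 1.23 | 0.26 |
| 3 terms | 3.28 v 0.82 | 0.12 |
| 4 terms | 2.46 v 0.62 | 0.06 |
| 6 terms | 1.64 v 0.41 | 0.02 |

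Why the rows fail: with no placebo case, a row needs 5 of 123 active. For 5 v 0, p = C(123,5)/C(246,5) = 0.030; for 4 v 0, p = 0.061. A six-term row expects fewer than two.

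Range over the assumptions:
- One dominant term with three quarters of the events: 0.75 × 8% = 6% v 0.75 × 2% = 1.5%, power 0.44 for that term alone.
- 5% v 1%: 0.41 grouped, 0.01 per term over four terms.
- 12% v 3%: 0.81 grouped, 0.15 per term over four terms.
- Two continuing doses pooled (246 v 123), 8% v 2%: 0.74 grouped.

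**The case against.** **On ECG.** The general rules in SAP 4.1 leave room for an ECG summary and a shift table. Protocol 9.4.3 promises descriptive summaries of vital signs and laboratory data only, so the SAP drops no promised ECG table. The listing is by treatment group and targets the clinically important cases, so they could be counted by hand against the as-treated number. All of this is true. But a hand count is not a planned output, covers one category only, and lacks baseline status and the number with an ECG. The conditional general rule does not displace a specific section that names a listing.

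**On hypersensitivity.** A reader might infer that no difference between arms could be seen. The documents do not support that. Protocol 8.2.5.2 has these reactions recorded as AEs or SAEs. SAP 4.2.10.7 tabulates AEs, SAEs, possibly related SAEs and AEs leading to discontinuation by arm, by SOC and preferred term, and sends them to the IDMC. Protocol 8.3.4 prefers a diagnosis to a list of symptoms, which limits scatter. SOC rows count each subject once within a class, although they mix in other events.

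A reader might also infer that rare terms are lost below the 5% cut for the most common events. They are not: that table is additional, and the full SOC and preferred term tables have no threshold.

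The power figures rest on assumed rates and splits, and SAP 4.2.10.7 plans counts and percentages, not tests. They show direction and rough size only.

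**On the IDMC.** A reader might infer that the committee will not see ECG or vital sign data, since the SAP places both at final analysis (for vital signs, "tables and listings will be based on the as-treated population and presented for each treatment group at final analysis"). SAP 1.2 says a separate charter governs the committee and that its report draws on some of the SAP's outputs. The charter is not available, so this cannot be settled.

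**Conclusion.** The point holds in two parts of different weight.

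- **ECG:** the comparison with placebo, an endpoint in both documents, has no planned output in the SAP's ECG section. That section is also at odds with the general rules in SAP 4.1. This rests on the text alone.
- **Hypersensitivity:** the comparison is planned but rests on separate SOC and preferred term rows. It is weakened, not removed. Under 8% v 2% with 123 per arm, power falls from about 0.60 grouped to between 0.26 and 0.02 per term for an even split over 2 to 6 terms. It falls only to 0.44 if one term takes three quarters of the events.

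No efficacy conclusion is affected. This is a cheap improvement that lets the trial meet its own safety objective.

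**What to change.** - **SAP 4.2.10.10:** replace the listing-only plan with a by-arm shift table of ECG status (normal; abnormal, not clinically significant; abnormal, clinically significant). Show baseline to worst and baseline to last on-treatment value, with the number of subjects with an ECG as denominator. Keep the listing. This uses the variable already defined in 3.3.5.4 and resolves the tension with 4.1.
- **SAP 4.2.10.7:** add a by-arm table of number and percentage of subjects on a pre-specified MedDRA grouping: SMQ Hypersensitivity (narrow), SMQ Anaphylactic reaction, and a named list of immune-complex terms fixed before unblinding.
- **IDMC reports:** include both tables where the charter allows.

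Cost: two additional tables from data already collected, and agreement on the immune-complex term list before unblinding. No extra visits or assessments are needed.
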